| Assess the impact of CAPTURE education and patient-level CAPTURE information on clinician interventions specific to smokers who are CAPTURE+. | Proportion of CAPTURE+ participants currently smoking at the baseline study visit who have any of the components of the Aim 3 primary endpoint or any of the following occur within 12 months of baseline (evaluated as a composite endpoint and as individual endpoints): 1) clinician counseling or recommendation for smoking cessation, 2) referral to a smoking cessation program, 3) referral to a smoking quit line, and 4) newly prescribed medication for smoking cessation. |
| Determine the impact of CAPTURE education and patient-level CAPTURE information on patient symptoms, exacerbations, hospitalizations, and mortality among CAPTURE+ patients. | In CAPTURE+ participants, change in CAT score between baseline and follow-up at 12 months after baseline, and proportion of patients who experience exacerbations, hospitalizations, or mortality within 12 months of baseline. |
| Determine the impact of CAPTURE education and patient-level CAPTURE information on identification and management of patients with respiratory burden. | All of the above endpoints for Aim 3, in the population of participants defined by each of the following instead of CAPTURE+ status: 1) clinically significant COPD, 2) spirometric COPD, 3) preserved ratio, impaired spirometry (PRISM), and 4) symptomatic non-obstructed (SNO). |
| Determine the potential impact of SARS CoV-2 infection on clinical actions taken in response to CAPTURE screening. | All of the above endpoints for Aim 3, in all of the analysis populations named above, separated into cohorts based on enrollment date and the degree to which follow-up may have been affected by the SARS-CoV-2 pandemic. |

6 Study Methods for Cluster Randomized Trial (CAPTURE Protocol Aim 3)

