9.4 Covariates and Subgroups

The effect of the CAPTURE intervention will be explored in predefined subgroups of interest with results tabulated (estimated difference in average proportion of CAPTURE+ patients per practice meeting composite endpoint between intervention arms by subgroup, corresponding 95% confidence interval and p-value) as well as displayed via forest plots. These analyses will proceed similarly to that described for the primary endpoint in section 11.1. Individual-level covariates used to define subgroups of interest are categorical age (45-59 years, 60-69 years, 70-80 years), gender (Male, Female), race (American Indian/Alaska Native, Asian, Native Hawaiian or Other Pacific Islander, Black or African American, White, Unknown or Not Reported), ethnicity (Hispanic/Latino, Non-Hispanic/Latino, Unknown or Not Reported), educational status (Less than High School Graduate, High School Graduate/GED, Vocational/Some College, College Degree, Professional/Graduate Degree, or Not Reported), insurance status (private, public, none), living arrangements (alone, not alone), employment status (working, not working, unknown), smoking status (Current, Former, Never), asthma history, baseline respiratory medications (short-acting bronchodilator, maintenance respiratory medication, or none), cardiac morbidity, COPD Assessment Test (CAT) score (10 or above versus less than 10), BMI (Below 25.0 [Normal/Underweight], 25.0-29.9 [Overweight], 30.0-39.9 [Obese], 40.0 and Above [Severely Obese]), as well as cohorts defined in section 6.1 (Spirometrically Defined COPD, Clinically Significant COPD, Mild COPD, No COPD by Spirometry, PRISm, and SNO). Practice level covariates include practice type (Part of large health system/ACO/similar, Part of academic medical center/health system, Federally Qualified Health Care Center, Independent practice, Other), location (Rural, Non-rural), being a residency site, having in-house spirometry, and number of MD/DO/NP/PA primary care clinicians (0-4, 5-9, 10 or More). Because of the possible impact of the SARS-CoV-2 pandemic on study outcomes, these analyses will be repeated in subgroups defined by whether the one-year follow-up period had entirely elapsed by March 19, 2020 (date when PBRNs paused study enrollment due to SARS-CoV-2); that is, the analyses will be repeated separately in the cohort with baseline visit completed on or before March 19, 2019, and separately in the cohort with baseline visit completed after March 19, 2019. Chart review and patient follow-up survey need not be completed by March 19, 2020 for a patient to be categorized as having pre-pandemic follow-up for this subgroup analysis.

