13.1 SARS-COV-2 Impact on Study Enrollment, Follow-up and Power

We have performed additional analyses for the CAPTURE DSMB regarding the impact of SARS-COV-2 on study power for the cluster randomized clinical trial described in Aim 3 of the CAPTURE protocol, summarized in a Memo dated March 30, 2020. Sections of the memo relevant to the SAP are repeated below.

At the time of placing enrollment on hold, the CAPTURE study was ahead of enrollment projections with a goal of completion of all patient enrollment by January 31, 2021. Table 1 displays enrollment data for each of the CAPTURE study's six enrolling PBRNs as of March 19, 2020, the date the last of

the six PBRNs temporarily stopped enrollment.

Table 6.

| PBRN site | Date enrollment put on hold | Number of practices enrolled as of 19MAR2020 (goal) | Number of patients enrolled as of 19MAR2020 (goal) | Estimated date of resumption of enrollment |
|-----------|-----------------------------|---|--|--|
| A | 13MAR2020 | 15 (20) | 663 (1000) | Indeterminate |
| B | 16MAR2020 | 15 (20) | 750 (1000) | Indeterminate |
| C | 16MAR2020 | 9 (20) | 431 (1000) | Indeterminate |
| D | 19MAR2020 | 6 (8) | 280 (400) | Indeterminate |
| E | 13MAR2020 | 11 (20) | 468 (1000) | Indeterminate |
| F | 16MAR2020 | 12 (13) | 446 (650) | Indeterminate |

As of April 1, 2020, none of the sites has an estimate of when enrollment will be able to resume. This information will be added as soon as such information becomes available.

Projected Enrollment Impact

To facilitate planning, projections on patient and practice enrollment impacts for Aim 3 have been developed. These projections are based on several assumptions.

1. Monthly enrollment rates of 100 or 125 patients as continuation and 5 new practices enrolled per month, consistent with prior data.
2. Two, four and six-month delays in enrollment.

Table 7.

| Enrollment suspension length assumption | Enrollment re-start date | Enrollment rate/month | Total number of participants (practices) enrolled by 31JAN2021 | Total number of participants enrolled by 31MAR2021 |
|---|--------------------------|-----------------------|--|--|
| 2 months | 1-Jun-20 | 100 | 3850 (100) | 4050 |
| 4 months | 1-Aug-20 | 100 | 3650 (100) | 3850 |
| 6 months | 1-Oct-20 | 100 | 3450 (90) | 3650 |
| 2 months | 1-Jun-20 | 125 | 4050 (100) | 4300 |
| 4 months | 1-Aug-20 | 125 | 3800 (100) | 4050 |
| 6 months | 1-Oct-20 | 125 | 3550 (90) | 3750 |

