We evaluated other scenarios including being able to increase enrollment to 150 patients per month with delays of two, four and six months and ending enrollment in January 2021 and March 2021.

Impact on Follow-up

The tables below present information on the initiation dates of the 12-month medical record abstraction by PBRN and the information on 12-month patient survey follow up as of March 25, 2020.

Table 8. 12-month Medical Record Abstraction (As of March 19, 2020)

| PBRN Site | Original ideal date of starting for 12- month medical records abstraction |
|-----------|---|
| A | 23MAR2020 |
| B | 30MAR2020 |
| C | Unknown |
| D | Unknown |
| E | 06APR2020 |
| F | No eligible patients until September 2020 |

Table 9. 12-month Patient Survey – COPD Foundation As of 3/25/2020

| | |
|---------------------------|-----------|
| Number Eligible | 380 |
| Phone Only | 118 |
| Email | 256 |
| Mail Only | 6 |
| Completed 12 Month Survey | 248 (65%) |
| Web | 84 |
| Phone | 134 |
| Mail | 30 |
| Mailed Surveys | 120 |
| Lost to Follow-Up | 20 |

Since all surveys are done by email, telephone call or mailings, there are no planned disruptions of the 12-month follow up patient surveys. All staff triggering email surveys, making telephone calls or preparing mailings are working from home.

Impact on Power

The goal of Aim 3 is to define the impact of CAPTURE information provided to clinicians in identifying and managing patients with respiratory symptoms (CAPTURE+) across a broad range of primary care settings. This Aim depends on the overall number of patients identified who are CAPTURE+, the number of practices enrolled as well as the ability to complete longitudinal follow-up.

Calculations were performed assuming 10 CAPTURE+/practice based on 67 total practices with > 1 CAPTURE+ patients (actual current state) taking into account loss of power due to variable cluster sizes. These data suggest that we are on track for having a well powered study for the primary analysis, even if additional data is difficult to obtain post-COVID crisis.

Table 10. Overall power to detect a difference in rate of meeting primary endpoint in CAPTURE group vs usual care, assuming 5% performance rate in usual care; 67 total practices; 10 CAPTURE+/practice

| Improvement over usual care | +7.5% | +10% | +15% | +25% | +50% |
|-----------------------------|-------|------|-------|-------|-------|
| ICC=0.05 | 0.76 | 0.92 | >0.99 | >0.99 | >0.99 |

| | | | | | |

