14.2 New SARS-COV-2 Inspired Analyses

The SARS-COV-2 pandemic has affected patient and practice enrollment and will potentially affect practice patterns moving forward. As part of the next protocol revision, the CAPTURE study plans to collect additional SARS-COV-2 inspired patient and practice information. This is a placeholder to update analyses once the next version of the protocol is complete. Of particular note will be analyses of additional data collected in response to SARS-COV-2 and analyses studying trends of 12-month outcomes that account for calendar time of collection

Protocol: N/A

SAP: 10.2.1 Secondary analyses of primary outcome

Additional sensitivity analyses will be conducted to assess the influence of the SARS-COV-2 pandemic on primary and secondary analyses. For the purpose of these analyses, we assume that participants who have completed their 12-month visit by March 19, 2020 provided baseline and 12-month follow-up measures that were unaffected by SARS-COV-2. We define an indicator variable SARS-COV-2=0 if a participant's baseline and 12-month follow-up measures were unaffected by SARS-COV-2 or SARS-COV-2=1 if participant's baseline or 12-month follow-up measures were affected by SARS-COV-2. All primary and secondary analyses will be repeated in the two cohorts defined by SARS-COV-2=1 or SARS-COV-2=0.

Protocol: N/A

SAP:10.2.2 Efficacy analyses of secondary outcomes**15 References**

1. Gosset, W.S. [Student, pseud.] 1908. The probable error of a mean. *Biometrika* 6: 1-25.
2. Pearson, K. 1900. On the criterion that a given system of deviations from the probable in the case of a correlated system of variables is such that it can be reasonably supposed to have arisen from random sampling. *Philosophical Magazine*, Series 5, 50: 157-175
3. Fisher, R.A. 1935. The logic of inductive inference. *Journal of the Royal Statistical Society*, Series A, 98: 39-54.
4. Liang, K.-Y. and Zeger, S.L. (1986) Longitudinal data analysis using generalized linear models. *Biometrika*, 73, 13-22.
5. Fitzmaurice, G. M., Laird, N. M., and Ware, J. H. (2011). *Applied Longitudinal Analysis* (2nd ed.) Hoboken, NJ: John Wiley and Sons.
6. Van Buuren, S. (2018). *Flexible Imputation of Missing Data* (2nd ed.) Boca Raton, FL: CRC Press.
7. Van Buuren, S., and Groothuis-Oudshoorn, K. (2011). mice: Multivariate Imputation by Chained Equations in R. *Journal of Statistical Software*, 45(3), 1-67. URL <https://www.jstatsoft.org/v45/i03/>.

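### SAP 9.4 reduces the degree of pandemic exposure to none versus any, so its later cohort mixes patients seen before the enrolment pause with patients enrolled after it

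*SAP*

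**What the plan says.** The last secondary endpoint in SAP 5.1, Table 1 (also in the protocol synopsis and Protocol section 3) wants every Aim 3 endpoint in every analysis population, "separated into cohorts based on enrollment date and the degree to which follow-up may have been affected by the SARS-CoV-2 pandemic". The linked objective is the pandemic's impact on clinical actions taken in response to CAPTURE screening.

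SAP 9.4 carries this out with a yes/no rule, "whether the one-year follow-up period had entirely elapsed by March 19, 2020", restated as baseline on or before 19 March 2019 "and separately in the cohort with baseline visit completed after March 19, 2019". It adds that the chart review and survey need not have been finished by March 2020.

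SAP 14.2 defines a second 0/1 indicator. It is based on having completed the 12-month visit by 19 March 2020, and "All primary and secondary analyses will be repeated in the two cohorts defined by SARS-COV-2=1 or SARS-COV-2=0". The only graded idea in either document is there too: "analyses studying trends of 12-month outcomes that account for calendar time of collection". That section calls itself a placeholder and gives no model.

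**The concern.** The composite endpoint is triggered by a result handed to the clinician around the baseline visit. Protocol 6.3 aims to share it at that visit so that the clinician can act promptly. A patient enrolled in, say, summer 2019 had the visit and the result months before any disruption. A patient enrolled after the pause had the visit, the result and the whole follow-up year in the pandemic. SAP 9.4 gives both the same label.

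If disruption changes clinician response more when more of the year is disrupted, the pooled later estimate lies between the two groups and closer to the early cohort than the fully exposed patients would be. A reader comparing the two cohort results would then see only part of any pandemic effect, and the objective would be answered less clearly than the data allow.

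**Working it through.** **Dates.** Baseline on 20 March 2019 plus 365 days is 19 March 2020, because 2020 is a leap year. That is 0 days after the cut (1 day if the year ends on the calendar anniversary). Baseline on 19 March 2020 gives 365 days after it. Both patients are in the later cohort.

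**Plan's own figures.** The SAP gives no size or power for the pandemic cohorts, so there is nothing to reproduce there. SAP 13.1, Table 6 sums to 663 + 750 + 431 + 280 + 468 + 446 = 3,038 patients enrolled by the pause. The lowest projection in Table 7 reproduces from a rounded start: 3,050 + 4 months × 100 = 3,450.

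**A point that needs no selection assumption.** SAP 13.1, Table 8 says PBRN F had nobody eligible for 12-month record abstraction until September 2020. Its 446 patients therefore enrolled from about September 2019 up to the pause. All had their index visit before the pause, and all fall in the later cohort.

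**Patients enrolled in the year before the pause (A).** SAP 13.1, Table 9 (25 March 2020) gives "Number Eligible | 380" for the 12-month survey. Take these as the selected patients who had reached 12 months. Early patients = 380 / (fraction selected for follow-up), and A = 3,038 − early.

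- Low selection fraction: SAP 13.1 assumes 10 CAPTURE+ in each of 67 practices, so 670 / 3,038 = 22.1%. Adding the 5% random sample of the rest gives 0.221 + 0.05 × 0.779 = about 0.26. This leaves out patients selected on spirometry alone, so it is a floor. Early = about 1,464; A = about 1,574.
- High selection fraction, assumed 50%: early = 760; A = 2,278.

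**Patients enrolled after the pause (B).** 3,450 − 3,038 = 412 at the low end. 5,000 − 3,038 = 1,962 if the full target is reached.

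**Make-up of the later cohort.** Share enrolled before the pause = A / (A + B). Mean share of follow-up after 19 March 2020 = (0.5A + B) / (A + B), where 0.5 assumes uniform entry over the year.

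| Selected | A | B | Share enrolled before pause | Mean exposed share |
|---|---|---|---|---|
| 26% | 1,574 | 412 | 0.79 | 0.60 |
| 26% | 1,574 | 1,962 | 0.45 | 0.78 |
| 50% | 2,278 | 412 | 0.85 | 0.58 |
| 50% | 2,278 | 1,962 | 0.54 | 0.73 |

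The early cohort has exposure 0 and patients enrolled after the pause have exposure 1. If the effect were proportional to exposure, comparing the two SAP cohorts would show about 58-78% of the full change.

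**Sensitivity to timing.** Suppose actions cluster soon after baseline, with an assumed half-life of 1 to 6 months. The mean exposed weight of the A patients then falls from 0.50 to 0.12-0.39. The later cohort's value becomes (0.12 × 2,278 + 412) / 2,690 = 0.25 at one end and (0.39 × 1,574 + 1,962) / 3,536 = 0.73 at the other.

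**The two SAP rules compared.** Take baseline on 1 March 2019 with the survey returned on 25 March 2020 (day 390, inside the 365 ± 30 window). This patient is early under 9.4 but affected under 14.2. Take baseline on 10 April 2019 with the survey returned on 15 March 2020 (day 340). This patient is in the later cohort under 9.4 but, on 14.2's completion rule, counts as unaffected. The rules disagree in both directions.

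**The case against.** The strongest reply is that the main product of such a sensitivity analysis is a set of patients untouched by the pandemic, and SAP 9.4 delivers that set cleanly. This stands. The mixing affects only the later estimate.

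The endpoint wording fixes no number of levels, so none versus any is a coarse reading rather than a breach. That also stands. It makes this an improvement to the plan rather than a correction of an error.

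The figures are soft, and this is right too. No selection rate is documented. Amendment 2.0 kept in follow-up the patients already selected under wider criteria, which points to a higher early selection rate and so a larger A. The survey window is ± 30 days, so some of the 380 may have had baseline after 19 March 2019, which would also enlarge A.

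A reader might infer that the SAP plans a test of the pandemic effect that this grouping would spoil. It does not: the analyses are repeated separately, with no between-cohort test and no arm-by-period interaction.

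A reader might also take early versus post-pause as a clean pandemic contrast. The documents do not support that. PBRN F has no early patients, the CAPTURE module was to be revised after Aim 2, and practices enrolled in the pandemic received added education content (Protocol 6.1.1). Such a difference would mix pandemic, network and intervention version.

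**Conclusion.** The point holds as a modest one. One open-ended later cohort spans zero to full pandemic exposure, and nothing else in the SAP specifies a finer grouping. The direction of the dilution rests on one assumption, that the pandemic effect grows with exposure.

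The size is not in the documents. The ranges of 45-85% and 0.58-0.78 rest on selection of 26-50%, uniform entry, the 380 being all selected patients at 12 months, and a final total of 3,450-5,000. Early clustering of actions would lower the exposed share further.

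It would go too far to say that a real pandemic effect would be hidden, or that the trial's main result is biased. Under these assumptions the change is attenuated, not erased. The primary analysis and its power are untouched, and SAP 9.7 already asks for caution with unadjusted secondary and exploratory p-values.

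**What to change.** In SAP 9.4, keep the early cohort and split the later one by baseline date: 20 March 2019 to 19 March 2020, and after enrolment resumed. Report all three.

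Optionally, add an exploratory arm-by-f term to the GEE, where f is the fraction of the 365-day window falling after 19 March 2020: (baseline date + 365 days − 19 March 2020) / 365, held between 0 and 1.

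Adjust for PBRN where feasible. State that early versus post-pause differences also reflect network mix and education content.

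In SAP 14.2, replace the completion-based indicator with the same date rule, so that the two sections agree, and either specify or delete the calendar-trend placeholder.

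The work is one variable derived from the baseline date and a few lines of SAP text. SAP 9.2 requires such decisions to be documented before lock and unblinding; if that point has passed, label the split as added afterwards. The price is smaller cohorts and wider intervals, so the three estimates should be read descriptively.

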
9.5 Missing Data

Baseline data, except for spirometry measurements, are expected to have few or no missing values. Baseline spirometry measurements are expected to be missing for a small portion of patients due to patient refusal/inability, administration error, or spirometry measurements having insufficient quality. Data from the 12-month medical record review are expected to be missing for a small portion of patients (among those selected for follow-up) due to various problems accessing the medical record. Data from the 12-month patient survey are expected to be missing for a significant portion of patients due to patients not returning completed surveys.

Any missing data or data anomalies will be communicated to the site(s) for clarification/resolution. We will summarize the extent of missing data by intervention group. Patient demographics, other baseline characteristics, and available 12-month follow-up data will be compared between those with and without complete follow-up data, among those who were prospectively selected for follow-up, overall and by intervention group.

The primary analysis of the primary and secondary endpoints will be among those with complete follow-up (complete data for the relevant portions of both the chart review and follow-up survey).

For each Aim 3 endpoint that is collected via both medical record review and patient survey, sensitivity analyses will be conducted by imputing missing outcome data using different assumptions and applying the primary analysis method to the resulting data sets. Sensitivity analyses will include

1. Imputation of negative responses (i.e., responses indicating that the outcome has not occurred) for all missing patient survey responses, followed by analysis of all patients with medical record review data
2. Imputation of positive responses (i.e., responses indicating that the outcome has occurred) for all missing patient survey responses, followed by analysis of all patients with medical record review data; and
3. Multiple imputation of all missing outcome data using the observed outcomes and covariates, as described below, followed by analysis of all patients selected for follow-up.

Multiple imputation of missing values in the baseline and 12-month follow-up data will be used to create 20 complete data sets. The set of patients included in each data set will be all of those selected for 12-month follow-up. The imputation method will be multivariate imputation by chained equations (MICE)⁶ as implemented in the R package 'mice'⁷.

Missing values of baseline spirometry FVC % predicted and FEV₁ % predicted will be imputed using linear regression models with the following predictors: age, gender, height, race, education, BMI, CAT score, asthma history, short-acting bronchodilator use, maintenance respiratory medication, and any follow-up outcomes for which baseline spirometry measurements will serve as predictors (selection of those predictors is described below). Predicted FVC and FEV₁ volumes will be calculated from the NHANES reference equations, allowing for calculation of the FVC, FEV₁, and FEV₁/FVC corresponding to the imputed % predicted values as needed.

For the purpose of organizing the imputation procedures, the 12-month follow-up outcomes will be grouped as follows:

- Pulmonary care outcomes:
 - Spirometry referral/completion
 - New diagnosis of COPD
 - New prescription for respiratory medication
 - Referral to pulmonologist or other respiratory specialist
 - Pulmonary rehab referral/completion
- Flu vaccination:
 - Flu shot recommended/ordered/administered
- Smoker-specific outcomes:
 - Counseling/recommendation for smoking cessation
 - Smoking cessation program referral/completion
 - New prescription for smoking cessation medication
 - Referral to a smoking quit line

Missing values of follow-up outcome variables, all of which will be binary (yes or no), will be imputed

using logistic regression models. For each outcome variable, the predictors will include, minimally, the following:

- All other variables from the medical record review and follow-up survey within the same group of outcomes. That is, medical record review data will be used to impute missing follow-up survey data, and follow-up survey data will be used to impute missing medical record data.
- Intervention group interacting with CAPTURE status. Intervention group must be included to avoid bias when using the imputed data to estimate the intervention effect. Interaction with CAPTURE status is included because the intervention effect is hypothesized to depend on the different recommendations associated with being classified as CAPTURE+ vs CAPTURE-.

Additional baseline predictors for imputing outcome variables will be included in the imputation procedure based on examination of study data that are blinded with respect to intervention group (pooled across intervention groups), assessing the association of each baseline variable with 1) whether the outcome data is missing, and 2) the outcome itself (among those with complete outcome data). To avoid including extraneous predictors, which may cause problems in fitting the logistic regression models and generating accurate imputations, we will use only baseline predictors that are associated with *both* the outcome missingness *and* the outcome itself, for at least one outcome in the group, based on p-values <0.01 from t tests¹ and chi-square tests². These additional baseline predictors will be selected separately for the medical record review variables and for the follow-up survey variables.

Based on the study data on March 21, 2023, from study sites for which all follow-up data have been collected (representing about 84% of the patients selected for follow-up), the additional baseline predictors for each outcome group would be the following:

| Outcome variable(s) | Predictors for medical record review | Predictors for follow-up survey |
|---------------------------------|--|---|
| Pulmonary care outcomes | PBRN Practice type Practice size (# clinicians) Patient enrollment date Education | Race Education Health insurance Smoking status FEV ₁ % predicted |
| Flu vaccination | PBRN Practice type Practice is a residency site Race Ethnicity Education | PBRN Age Race Education Health insurance Ever had flu shot |
| Smoker-specific outcomes | PBRN Practice type Practice is a residency site Practice size (# clinicians) Education | PBRN |

